8.4.2 Sponsor Discontinuation Stopping Criteria

The Sponsor will review data on an ongoing basis and may, on discussion with the DMC, terminate the study for any clinically significant drug related safety signal (eg, serious hypersensitivity reactions or drug induced liver injury, etc.).

Premature termination of a study may also occur because of a regulatory authority decision, change in opinion of the IRB/EC, drug safety problems, or at the discretion of Sponsor . In addition, Sponsor retains the right to discontinue development of inclisiran at any time.

If a study is prematurely terminated or discontinued, Sponsor will promptly notify the investigator. After notification, the investigator must contact all participating subjects and the hospital pharmacy (if applicable) within 30 days of the notification. Final study visits should occur within 30 days of subject contact. As directed by Sponsor , all study materials must be collected and all care report forms (CRFs) completed to the greatest extent possible.

The Sponsor will inform the health authorities and the IRBs/EC that the study has been stopped and the reasons for doing so, within the locally applicable timelines.

9 Data Collection

An electronic data capture (EDC) system will be used for this study. All users will be trained on the technical features of the EDC as well as the content of the eCRF by qualified personnel prior to gaining access to the EDC. A UserID/Password will be granted after training. This ID is not to be shared amongst the study staff. All users must have a unique account to enter or review data. The eCRF should be filled out by the site 3 days after each visit. It is not expected that the eCRF will serve as source for any data collected in this study. If there is a reason for a site to do so, it must be approved by MDCO and documented in the site files.

This study will utilize the same EDC system used in the ORION-1 study to collect the data defined by this protocol, [REDACTED]. Data already collected for medical history, ongoing concomitant medications, and ongoing adverse events will be retained and utilized in analysis as defined by the SAP.

Prior to the database being locked, the investigator or designee will review, approve, and sign/date each completed eCRF. This signature serves as attestation of the investigator's responsibility for

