**Table 2-1 Summary of baselines**

Analysis category	Analysis	Baseline used	Explanation
Baseline Characteristics	Age*, weight, body mass index (BMI), country	Study entry of ORION-3	To provide a more accurate value of parameters that may change, baseline of ORION-3 is used.

	Estimated glomerular filtration rate (eGFR)	Last non-missing record prior to first study drug administration of ORION-3	To provide a more accurate value of parameters that may change, baseline of ORION-3 is used.
	Sex, race, ethnicity, height	Screening period of ORION-1	These values will not change or will not change significantly so baseline of ORION-1 is used.
	Medical history	Day 1 of ORION-1	Medical history is reported prior to the first treatment in ORION-1, after which any new medical conditions will be captured as AEs.
Prior and concomitant therapies	Concomitant Medications	Day 1 of ORION-3	Medications taken on or after Day 1 of ORION-3 will be considered as concomitant for ORION-3.**
Efficacy	Efficacy parameters in Group 1 (inclisiran only arm)	Baseline of ORION-1***	Due to residual efficacy from ORION-1, the true change from baseline should use baseline of ORION-1, i.e. prior to receiving any dose of inclisiran.
	Efficacy parameters in Group 2 (switching arm)	Baseline of ORION-3****	Placebo was given in ORION-1 and since treatment adjustments may have occurred during ORION-1 in lipid modifying therapies (LMT), baseline of ORION-3 will be used.
Safety	Adverse events	Day 1 of ORION-3	Previous AEs are collected in ORION-1, the gap period and the observation period so TEAEs in ORION-3 are collected from Day 1 (first dose) of ORION-3.
	Electrocardiograms (ECG)	Day 1 of ORION-3	To identify untoward change in ECG within ORION-3
	Safety laboratory parameters, vital signs	Baseline of ORION-3****	To identify untoward change in safety laboratory parameters and vital signs within ORION-3

\* Since age will not be re-collected in ORION-3, the age at ORION-3 baseline is inferred using the ORION-1 baseline:

- If the difference between consent date in ORION-3 and ORION-1 is greater than 365 days for a subject then 1 year will be added to the age at ORION-1 baseline;
- Otherwise, ORION-1 baseline age will be used.

\*\* Although all medications received 30 days prior to consent in ORION-1 through the EOS in ORION-3 will be reported, only medications taken on or after Day 1 of ORION-3 will be considered concomitant for ORION-3.

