### 2.7.1 Adverse events (AEs)

Adverse events will be summarized for every group specified above in [Section 2.7](#).

The most recent version of MedDRA before DBL will be used for coding AEs. An AE (classified as preferred term) will be counted as a treatment emergent AE (TEAE) if the AE started after the first treatment in ORION-3 or the AE was present prior to the first treatment in ORION-3 but increased in severity after initiation of study drug in ORION-3. Only TEAEs will be summarized in the tables, but the subject data listings will include all AEs.

The following summary tables will be presented:

- Overall Summary of TEAEs
- TEAEs by primary system organ class (SOC) and preferred term (PT)
- TEAEs by PT
- TEAEs by primary SOC, PT, and severity
- TEAEs related to study drug by primary SOC, PT
- Treatment Emergent Serious AEs (TESAEs) by primary SOC and PT
- TESAEs by PT
- TESAEs related to study drug by primary SOC, PT
- TEAEs leading to withdrawal of study treatment by primary SOC and PT
- TEAEs with a fatal outcome by primary SOC and PT
- TEAEs at the injection site by primary SOC and PT
- Clinically relevant TEAEs at the injection site (listed in [Appendix 5.3](#)) by PT

- TEAEs at the injection site by primary SOC, PT and severity
- Prespecified signs and symptoms at the injection site

If more than one event occurred with the same preferred term for the same subject, the subject will be counted only once for that preferred term, using the most severe occurrence for the summary by severity. For select tables, exposure-adjusted incidence rate (EAIR) will be calculated for subjects from the inclisiran only arm (Group 1), for the period from Day 1 (Day 1 of ORION-3) until EOS, [REDACTED]

EAIR is defined as the total number of subjects with the event / total exposure (years) \* 100%, where total exposure = sum of duration from start date of inclisiran injection in ORION-3 to the onset date of the event (the last visit/contact date will be used for the patients without the event).

TEAEs at the injection site include all TEAEs identified as being an injection site reaction on AE Case Report Form (CRF) or with “injection site reactions” as the high level term (HLT).

The following additional adverse events will be assessed (Refer to [Appendix 5.2](#) for the detailed definitions):

1. Hepatic events
  2. Renal events
  3. Hypersensitivity
  4. Neurological events and Neurocognitive disorders
  5. Ophthalmological events
- [REDACTED]

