#### 5.1.2 AE date imputation

Adverse events with incomplete dates will be categorized as treatment emergent unless there was sufficient specificity to the start/end dates to determine that the event began before the first dose of study drug.

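### The Group 1 EAIR stops the clock at AE onset, which gives negative exposure for any worsened pre-existing AE that keeps its pre-dose onset date

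*SAP*

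**What the plan says.** Three statements in SAP Section 2.7.1 bear on this.

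- **Who counts.** Besides events that start after the first ORION-3 treatment, a TEAE includes the case where "the AE was present prior to the first treatment in ORION-3 but increased in severity after initiation of study drug in ORION-3".
- **How time is counted.** The EAIR is the number of subjects with the event divided by total exposure in years, where "total exposure = sum of duration from start date of inclisiran injection in ORION-3 to the onset date of the event". For everyone else, "the last visit/contact date will be used for the patients without the event".
- **Where it is used.** The EAIR is planned for selected tables, in Group 1, from Day 1 of ORION-3 to end of study. The tables are not named in the visible text, and some text next to this statement is redacted.

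Pre-dose events will be in the data. SAP Table 2-1 says "Previous AEs are collected in ORION-1, the gap period and the observation period". Protocol Section 9 says that the same data capture system as in ORION-1 is used and that "ongoing adverse events will be retained and utilized in analysis as defined by the SAP".

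The only date rule for adverse events, SAP Section 5.1.2, concerns classification: "Adverse events with incomplete dates will be categorized as treatment emergent unless there was sufficient specificity to the start/end dates". It sets no date for the EAIR.

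**The concern.** The numerator and the denominator rest on different dates. The TEAE definition turns on when severity increased; the exposure formula turns on when the event began. For a new event the two coincide. For a worsened pre-existing event, onset lies before the first injection by definition, so the interval from injection to onset is below zero.

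Such a subject counts as one event and also reduces the person-time supplied by the others. The direction is fixed: the denominator shrinks and the EAIR rises. Real time at risk between Day 1 and the worsening is lost as well.

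Long-term safety and tolerability in Group 1 is a secondary objective, and the EAIR is specified for that group, so its derivation should not depend on an unstated programming choice.

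**Working it through.** The documents report no EAIR value, so there is no figure to reproduce. The check is whether the visible text repairs the mismatch and, if not, how large the effect could be.

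**Step 1. Is there a repair in the text?** No visible sentence replaces onset with a worsening date, floors the duration at zero, or excludes these subjects. Protocol Section 10.3.4.1 assigns pre-dosing events to the ORION-1 safety evaluation, but the same section counts an event present at Day 1 that later increased in severity as a TEAE, so it does not remove this class.

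**Step 2. Contribution of one subject.** Onset 30, 180, 360 or 540 days before Day 1, divided by 365.25, contributes −0.08, −0.49, −0.99 or −1.48 person-years.

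**Step 3. Effect on a rate.** Let N be the subjects in Group 1, F the follow-up in years, E the subjects with the event, k those among them whose event began before Day 1, t the mean time to a new or worsened event, and b the mean lead time of onset before Day 1.

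- As written: 100 × E / [(N−E)F + (E−k)t − kb]
- Floor at zero: 100 × E / [(N−E)F + (E−k)t]
- Worsening date: 100 × E / [(N−E)F + (E−k)t + kt]

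Inputs from the documents: 382 enrolled (Protocol, Amendment 5 rationale); 374 of 501 randomized to inclisiran in ORION-1 (Protocol 1.2.2); end of study at Day 1440, so F = 1439/365.25 = 3.94.

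Assumptions: N = 382 × 374/501 ≈ 285 (Group 1 size is not given); b = 1 year; k about 10% of E; t = F/2 = 1.97 years for a single preferred term (PT) and 0.6 years for any TEAE.

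| Row | E | k | As written | Zero floor | Worsening date | As written vs worsening date |
|---|---|---|---|---|---|---|
| PT in 10% of subjects | 28 | 3 | 2.64 | 2.64 | 2.62 | +0.8% |
| Any TEAE in 90% | 256 | 26 | 113.15 | 101.49 | 95.57 | +18.4% |

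(Rates per 100 patient-years.)

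For the any-TEAE row:

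- (29 × 3.94) + (230 × 0.6) = 252.25 patient-years, the zero-floor denominator.
- As written: 252.25 − 26 = 226.25.
- Worsening date: 252.25 + 26 × 0.6 = 267.85.

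A zero floor alone removes the negative time but still leaves this row 6.2% high (101.49/95.57).

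**Step 4. Range.** With F = 3.0 or 3.94 years, b = 0.25 to 1.5 years, and k = 5% to 20% of E (at least one subject), the excess over the worsening-date rule is:

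- PT in 2% of subjects: 0.2% to 0.4%
- PT in 10%: 0.2% to 2.3%
- Any TEAE in 90%: 4% to 80%
- Any TEAE in 97%: 6% to 150%

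**Step 5. Second route for any TEAE.** Take a constant first-event hazard λ and a share p of all subjects whose first TEAE is a worsened pre-existing event. Mean person-time is (1 − exp(−λF))/λ, which is 0.665 years at λ = 1.5 and 0.500 at λ = 2.0. The formula as written removes p(1/λ + b). With b = 0.5 to 1.5 years:

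- p = 2%: loss of 0.020 to 0.043 years, excess 4% to 9%
- p = 5%: excess 10% to 25%
- p = 0.2%: excess about 0.4% to 0.8%

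Both routes agree: negligible for rare terms, and possibly visible where most subjects stop accruing time early. The size is driven by the share of worsened events, which the documents do not give.

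**The case against.** The strongest reply is that the problem may never arise. The SAP defines a TEAE at preferred-term level and provides for several records of the same term in one subject, counting the most severe. That fits a convention in which worsening is entered as a new record with its own post-dose start date. The EAIR period is also stated to run from Day 1 to end of study, and Table 2-1 says ORION-3 TEAEs are collected from Day 1, so the event was plausibly meant as the treatment-emergent one. This stands as a limit: under that convention the effect is nil. It does not settle the matter, because neither document states the convention and the formula names the onset date.

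A reader might infer that the headline Group 1 rates will be materially inflated. The documents do not support that. The tables carrying an EAIR are not named, so an any-TEAE or system-organ-class EAIR cannot be assumed. Retaining ongoing ORION-1 events makes pre-dose onsets possible, but it does not show that any of them worsened.

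It is also fair that a worsening date may not have been collected, and that SAP Section 2.7 rules out imputing missing safety data. That bears on how the fix is written, not on whether the formula is sound. Finally, any error would overstate harm rather than hide it.

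**Conclusion.** The point holds in conditional form. Read literally, SAP 2.7.1 gives negative person-time to a subject whose TEAE is a worsened pre-existing event recorded with its pre-dose onset, and this biases the Group 1 EAIR upward.

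The effect is nil if worsening has its own record and about 1–2% or less for individual preferred terms (2.3% at the extreme of the ranges tried). It is possibly several percent or more for an overall or common-event row, if EAIR is produced for one. These sizes are illustrations: Group 1 size, number of worsened events, their lead times and the list of tables are all assumed or unknown. The rate is descriptive, with no test or decision rule attached in the visible text, so this is a minor but inexpensive correction.

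**What to change.** In SAP 2.7.1, end exposure at the date the event first became treatment-emergent. That is the onset date if it falls on or after the first ORION-3 inclisiran injection, and otherwise the date of the first recorded severity increase after that injection. Set a minimum duration of 1 day.

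Where no worsening date is recorded, use the date of the first visit recording the higher severity or, failing that, the 1-day minimum. State this as an exception to the no-imputation rule in SAP 2.7.

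The cost is a short text change and one extra derivation, with an approximate date for some events. The 1-day fallback prevents negative time but still drops the time at risk before worsening, so it should be the last resort. If worsening is always entered as a new record, saying so in the SAP shows that the rule changes nothing.

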4.4.2 Individual Subject Dosing Stopping Criteria

Subjects will have clinic visits at regular intervals. The following individual dosing stopping criteria will be followed:

1. Dosing with study medication (inclisiran or evolocumab) may be temporarily discontinued or stopped for intolerable AEs, or if the Investigator believes that continuing dosing will be detrimental to the subject's mental or physical health. This includes severe or serious reactions at the injection site and any anaphylactic type reactions.
2. Subjects with persistent and unexplained increases in transaminases (ALT or AST) >3x ULN or with bilirubin increases >2x ULN from a normal baseline on two consecutive occasions at least 4-7 days apart by repeat test must be discontinued from study treatment

and asked to complete the remainder of the scheduled visits without receiving study medication (inclisiran or evolocumab).

3. Subjects with unexplained creatine kinase (CK) values $>5 \times$ ULN confirmed by repeat test, for whom the CK elevation is associated with muscle pain, muscle tenderness and/or muscle weakness, or new onset renal dysfunction, must be discontinued from study treatment and asked to complete the remainder of the scheduled visits without receiving study medication (inclisiran or evolocumab).

5 Treatment of Subjects

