## **2.4 Treatments (study treatment, rescue medication, concomitant therapies, compliance)**

### **2.4.1 Study treatment / compliance**

Study drug administration will be summarized for inclisiran and evolocumab separately, overall and by visit. For inclisiran, the summary will include number of doses, actual dose for each injection, injection volume received, location for each injection, and occurrence of any medication errors. For subjects in Group 2 (switching arm), inclisiran administration after transitioning to inclisiran will be summarized by transition groups.

Duration of exposure to inclisiran in ORION-3 and cumulative exposure to inclisiran from ORION-1 through ORION-3 will be summarized. Duration of exposure to inclisiran will be calculated as: minimum of (Date of last dose of inclisiran – Date of first dose of inclisiran + 180) and (Date of last known visit/contact – Date of first dose of inclisiran). Patient years exposure (ORION-3 and cumulative) to inclisiran will also be summarized, which is calculated as (sum of duration of exposure to inclisiran)/365.25.

For evolocumab, the number and percent of subjects who have evolocumab administrations will be summarized for each planned time point of injection. Number of injections and number of missed injections will also be summarized.

Summaries will be presented for the safety population by treatment group (Group 1 and Group 2). Select tables for Group 2 will be broken down by transition group (Transition 1 (staged) and Transition 2 (concurrent)).

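### The SAP's exposure-adjusted incidence rate divides by time on study, not by inclisiran exposure as SAP 2.4.1 defines it; report an on-treatment rate and relabel the current one

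*SAP*

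**What the plan says.** SAP 2.7.1 plans EAIRs for selected tables, which it does not list. For Group 1 they cover Day 1 to end of study. The rate is the number of subjects with the event divided by total exposure in years, times 100. The time is defined as "total exposure = sum of duration from start date of inclisiran injection in ORION-3 to the onset date of the event", and "the last visit/contact date will be used for the patients without the event". An adverse event counts as treatment emergent "if the AE started after the first treatment in ORION-3", or if it was already present and then worsened. Neither definition refers to the date of the last dose.

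SAP 2.4.1 defines duration of exposure to inclisiran differently, as the "minimum of (Date of last dose of inclisiran – Date of first dose of inclisiran + 180" days) and ("Date of last known visit/contact – Date of first dose of inclisiran"). Patient-years there are "sum of duration of exposure to inclisiran)/365.25".

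Protocol 4.4.2 says that subjects meeting the liver or CK stopping criteria must be discontinued from study treatment "and asked to complete the remainder of the scheduled visits without receiving study medication (inclisiran or evolocumab". Protocol 3.1 schedules visits to Day 1440.

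**The concern.** The SAP uses the word exposure for two different lengths of time. In the exposure summary it ends 180 days after the last injection. In the incidence rate it is follow-up time. The two part company for subjects who stop inclisiran and keep attending for more than 180 days afterwards, which Protocol 4.4.2 asks some subjects to do.

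Long-term safety and tolerability is a secondary objective (Protocol 2.2), and the EAIR is the only visible adverse-event rate that accounts for time. A reader of the report will take it as a rate per year on inclisiran. Where an event needs an injection, time long after the last one adds to the denominator with little chance of adding an event, so the rate comes out low as a description of treated time. Injection-site events are the clearest case, if they are among the selected tables. Protocol 1.2.3 names injection site reaction as the only event known to be attributed to inclisiran. For other events, experience on and after treatment is mixed under an on-treatment label.

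**Working it through.** The documents give no EAIR, event count or Group 1 size, so there is no planned figure to reproduce. The check applies both SAP formulas to the planned Group 1 schedule.

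**Inputs.** Dose days 1, 180, 360, 540, 720, 810, 990, 1170 and 1350, and last contact Day 1440 (Protocol 3.1). Formulas from SAP 2.4.1 and 2.7.1.

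**Step 1: one event-free subject who attends to Day 1440.**

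- SAP 2.4.1: min(last dose day − 1 + 180, 1440 − 1)
- SAP 2.7.1: 1440 − 1 = 1439 days, whenever dosing stopped

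| Last dose (day) | SAP 2.4.1 (days) | SAP 2.7.1 (days) | Difference (days) |
|---|---|---|---|
| 1 | 180 | 1439 | 1259 |
| 180 | 359 | 1439 | 1080 |
| 360 | 539 | 1439 | 900 |
| 540 | 719 | 1439 | 720 |
| 720 | 899 | 1439 | 540 |
| 810 | 989 | 1439 | 450 |
| 990 | 1169 | 1439 | 270 |
| 1170 | 1349 | 1439 | 90 |
| 1350 | 1439 | 1439 | 0 |

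The difference runs from 0 to 1259 days (1259/365.25 = 3.45 years). It is zero for full-course subjects. It is also zero for a subject who leaves within 180 days of the last dose: with last dose Day 360 and last contact Day 390, both formulas give 389 days.

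**Step 2: effect on the group denominator.** Assume that a fraction p stops and attends to Day 1440, that the others complete, and ignore the shortening of time by events. With d the difference from Step 1, the inflation over SAP 2.4.1 exposure is 1439/(1439 − p × d) − 1. It does not depend on the number of subjects.

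- p = 1%, stop after Day 360: 1439/1430 − 1 = 0.6%
- p = 2%, stop after Day 360: 1439/1421 − 1 = 1.3%
- p = 5%, stop after Day 360: 1439/1394 − 1 = 3.2%
- p = 5%, stop after Day 720: 1439/1412 − 1 = 1.9%
- p = 5%, stops spread evenly over the first eight doses (mean d = 5309/8 = 663.6): 1439/1405.8 − 1 = 2.4%
- p = 5%, stop after Day 180: 1439/1385 − 1 = 3.9%

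**Step 3: effect on the rate.** Assume a constant rate of 5.00 per 100 patient-years up to 180 days after the last dose, and p stopping after Day 360. Expected first events and expected time at risk then give:

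| Rate after that point | EAIR as written, p = 2% | EAIR as written, p = 5% |
|---|---|---|
| Zero | 4.94 | 4.84 |
| Halved | 4.97 | 4.92 |
| Unchanged | 5.00 | 5.00 |

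Limiting both events and time to last dose plus 180 days returns 5.00 in every row. Limiting the time alone, with the rate unchanged, overstates it: 5.06 at 2% and 5.16 at 5%.

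**The case against.** The strongest reply is that SAP 2.7.1 gives its own explicit definition, so a programmer has one unambiguous instruction, and that numerator and denominator agree: events are counted and time is accrued over the same period, Day 1 to end of study. That stands. The EAIR is valid as an on-study rate, and Step 3 shows no bias when risk does not change after stopping. A reader might infer that the treatment-emergent window never closes. It does close, at end of study. It simply has no end tied to the last dose.

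A second reply is that 180 days is not shown to be the end of the drug's effect. Protocol 1.2.2 reports LDL-C reduction lasting to 360 days, and SAP Table 2-1 refers to residual efficacy from ORION-1. This also stands. It is the reason to keep the on-study rate beside an on-treatment one. It does not explain why the SAP uses the 180-day limit for exposure in one section and none in another.

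Third, few subjects may be affected. The stopping rules in question are narrow, subjects are only asked to continue, and Protocol 1.2.2 reports a low incidence of AST, ALT and CK rises in ORION-1. This limits the likely size but leaves the label as it is.

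A reader might also treat it as an error that the patient-years in the exposure table will not match those behind the rates. They would differ in any case, because EAIR time stops at the event.

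**Conclusion.** The point holds as one of labelling and of a missing on-treatment rate. What SAP 2.7.1 calls total exposure is on-study follow-up, and no visible text reconciles it with SAP 2.4.1. The rate understates on-treatment incidence only for events whose risk falls after stopping.

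The group effect rests on an assumed fraction who stop and still attend to Day 1440: about 0.6% to 1.3% denominator inflation if 1% to 2% stop after Day 360, and about 2% to 3% at 5%, depending on when they stop. Very early stopping at 5% would take it to 3.9%.

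Two stronger readings are not supported. One is that the safety rates are substantially diluted: 10% to 20% stopping after Day 360 would give 6.7% to 14.3%, but nothing in the documents points to fractions of that order. The other is that injection-site rates will be understated. That follows only if those tables are among the ones selected for EAIR, which the SAP does not say.

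**What to change.** In SAP 2.7.1, add an on-treatment EAIR. Its time at risk runs from the first ORION-3 inclisiran injection to the earliest of event onset, last inclisiran dose plus 180 days (the rule already in SAP 2.4.1) and last contact. Its numerator counts only events with onset in that time. Keep the present calculation as a second row, labelled as incidence per 100 patient-years on study, so that later events of a long-acting drug are not lost. Change both sides of the on-treatment rate together, since capping the denominator alone would bias it upwards.

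The cost is a few lines of SAP text, one derived censoring date and one extra row in the selected tables. No data collection or clinical rule changes.
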